8. INTERVENTION DISCONTINUATION

Adverse gastrointestinal events associated with the consumption of ginger that require medical intervention (intravenous fluid administration, hospital admission) will prompt temporary suspension of enrollment and/or study interventions until a complete safety review is convened. Adverse reactions to inhaled methacholine that require hospital admission will prompt temporary suspension of enrollment and/or study interventions until a complete safety review is convened. Subsequent review of serious, unexpected, and related AEs by the DSMB, Independent Safety Monitor(s), IRB or the FDA may also result in suspension of further study interventions/administration of study product. The FDA retain the authority to suspend additional enrollment and study interventions/administration of study product for the entire study, as applicable.

Participants will continue to be followed with their permission if study intervention is discontinued. Temporary discontinuation of treatment would interrupt the consecutive 56 day treatment plan and thus subjects would be removed from the study. If a subject is removed from the study, evaluations related to any adverse events would be continued as defined in section 7.5 above.

9. STATISTICAL CONSIDERATIONS

9.1 General Design Issues

We hypothesize that the oral consumption of Pure Encapsulation® ginger extract (2g/day by adult patients with moderate to severe asthma despite normal maintenance medications, will have an improvement in their tolerance to inhaled methacholine or a reduction in lung inflammation over the 56 day treatment period.

This is a randomized, double blind, placebo-controlled design. Patients will have baseline measurements of their pulmonary function and inflammation status and will then be randomized to ginger extract or placebo. The same measurements of pulmonary function and inflammation status will be repeated at 28 and 56 days of ginger or placebo consumption. The durations of 28 and 56 days were chosen because it is hypothesized that the primary benefit of consumption of oral ginger will be an anti-inflammatory effect in

the lung that over time results in improved pulmonary function.

Primary hypotheses: are that the oral daily consumption of ginger will improve the tolerance to inhaled methacholine and/or a reduction in exhaled nitric oxide.

Secondary hypotheses: are that an additional measure of pulmonary function will improve (an increase in baseline FEV1) and/or that secondary measures of inflammation (eosinophilia, asthma associated cytokines) will improve.

Primary outcome measures: The primary outcome measures are methacholine (PD20) and exhaled nitric oxide. These outcomes will be measured at visit 3 (baseline) and visits 4 and 5 (days 28 and 56 of the oral ginger or placebo consumption).

Secondary outcome measures: A clinically significant increase in baseline FEV1 of 100ml. For subjects with eosinophilia (>300 cells/ul) a 32% decrease in blood eosinophils¹⁷, a 40% decrease in serum IL4^{18,19}, a 50% decrease in serum IL5²⁰ or a 75% decrease in serum IL13.²¹

9.2 Sample Size and Randomization

We utilized published literature to identify the magnitude of change in our primary outcomes that are clinically relevant. As illustrated in the table in section 3, we calculated a need of 14 subjects per arm for the methacholine measurement and 16 subjects per arm for the exhaled nitric oxide assessment (same subjects studied in methacholine and exhaled nitric oxide assays). Thus we need 16 subjects per arm and anticipate a 10% attrition rate overall requiring 36 subjects. As illustrated in the table in section 3, an enhanced tolerance to inhaled methacholine of 0.7X the doubling dose is considered clinically significant.¹² We anticipate a S.D. of 0.6 in both groups and aim to achieve 80% power at the 0.05 significance level. This requires 14 subjects for each of the two arms. For exhaled nitric oxide with baselines starting at >50ppb, a 20% decrease is considered clinically significant. We expect a S.D. of ~ 37 and aim to achieve 80% power at the 0.05 level and will thus require 16 subjects for each of two arms.

Treatment Assignment Procedures

Subjects will be randomized to treatment A or B in a blinded fashion using the randomization algorithm within REDCap. The randomization module in REDCap implements a defined randomization model within the project, allowing the site to randomize the subjects. In this module, randomization model is defined as Drug A and Drug B in a 1:1 ratio. Drug A and Drug B may refer to placebo or active drug, however they are left coded as such to ensure blinding. The module creates a template allocation table, which the user uses to structure the randomization table to be imported. The module also monitors the overall allocation progress and assignment of randomized subjects to ensure balanced proportions of active drug and placebo. Only one site member will be allowed randomization privileges, but the site will confirm, and lock the specific data field to ensure that no data is altered after randomization. There is no stratification, and there are no variable block sizes.

Trial randomization codes for each individual subject will be retained within the REDCap data set as treatment A or B. The independent statistician retains the identity of A or B and does not disclose this to the study conductors. The planned breaking of the code will occur after data analysis is complete. Unplanned breaking of the code will occur if a medical condition mandates such an action.

Ginger extract and placebo capsules have been pre-packaged and labeled with a code by the distributor (Atrium Innovations, Pure Encapsulations) and delivered to the research pharmacy at the Columbia University Medical Center. We do not anticipate any collected data offering evidence of a participant's assignment to a particular arm. All study data is collected objectively without an opportunity for the collected data to identify the study arm. For example, changes in methacholine PD20 and exhaled nitric oxide (primary outcomes) will vary over the course of the study in both ginger and placebo treated subjects. These variations will not be able to offer evidence of group membership and will only be informative after analysis in the aggregate.

The study PIs, [name], [name] are authorized to break the blind if there is a concern for subject safety, a serious adverse event or safety concerns raised by the DSMB. The PIs will contact the research pharmacy who will be holding the codes.

No stratification of the randomization will occur.

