1. STUDY OBJECTIVES

1.1 Primary Objective

The primary endpoints are a clinically significant improvement in tolerance to inhaled methacholine (PD20) or a clinically significant decrease in exhaled nitric oxide. A clinically significant increase in tolerance to inhaled methacholine is defined as a 0.7 increase in the doubling dose for inhaled methacholine from the subjects baseline. A clinically significant decrease in exhaled nitric oxide is defined as a 20% decrease in subjects starting at a baseline of >50 ppb or a decrease of 10 ppb for subjects starting at a baseline of <50 ppb.

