3. STUDY DESIGN

A placebo controlled, double blind, randomized clinical pilot study of mild to severe asthmatics treated in a 1:1 ratio with oral ginger 1 gm twice per day or matching placebo.

18 subjects will be assigned to each of two arms (ginger vs. placebo). This is defined by a power analysis requiring 16 subjects per arm and a 10% projected attrition rate. Subjects will be evaluated 5 times during the study, at screening, baseline methacholine testing, at the initial randomization visit and at days 28 and 56 while taking ginger or placebo.

The primary outcomes will be the improved tolerance to the bronchoconstrictive effect (reduced airway hyperresponsiveness) of inhaled methacholine (methacholine PD₂₀) or a reduction in exhaled nitric oxide. Secondary outcomes will include an improvement in baseline FEV1 of 100ml, a reduction in eosinophilia or a reduction in asthma associated serum cytokines. An additional secondary outcome will be defining the pharmacokinetic profile of active components of ginger in adult asthmatics.

Grant phase	Spec. Aim	Primary outcome	Clinically Significant Change [ref]	Means ± S.D; examples from literature [ref] (units)	Sample Size \group	# of groups	Sample size required	Sample Size required with 10% attrition
R61	1	Mch PD ₂₀ doubling dose	Increase of 0.7 in Mch doubling dose ¹²	1.07 ± 0.6 1.73 ± 0.6 (Mch doubling dose) ¹²	14	2 2g/day ginger placebo	28	32
	2	Exhaled nitric oxide	20% decr for >50 ppb or decr of 10ppb for <50ppb ¹³	74 ± 37 37 ± 34 (ppb) ¹⁴	16	2 2g/day ginger placebo	32	36 for aims 1&2

Outpatient; The John Edsall-John Wood Asthma Center at the Columbia University Medical Center

Individual enrollment: 78 +/- 7 days. Enrollment period 12 months, Entire trial (first subject screened to last patient completed): 20 months.

Screening/Run-In Period

Adults 18 and older, with physician diagnosed mild to severe persistent asthma will be screened. After reviewing and signing informed consent, subjects that fulfill inclusion and exclusion criteria will be invited to participate.

Day 0/Visit 1: Screening Visit: review of medical history, recording of medication use, physical exam by study MD or NP, scoring on ACT and basic spirometry before and after bronchodilator. Subjects will then be asked to continue their usual asthma medications for the 14-21 day run-in period.

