4. SELECTION AND ENROLLMENT OF PARTICIPANTS

4.1 Inclusion Criteria

Subjects must meet all of the inclusion criteria to participate in this study.

1. Adults aged 18 years and above, with mild to severe persistent asthma will be enrolled as defined by The NIH National Asthma Education and Prevention Program (NAEPP) Guidelines for Assessing Asthma Severity¹ (please see table page 9). Subjects will have asthma which is not optimally controlled as defined by Asthma Control Test (ACT) score, despite the current use of inhaled corticosteroids with or without inhaled long-acting beta agonists.
2. Treatment with inhaled corticosteroids (ICS) +/- long acting β -agonists/long acting muscarinics and montelukast;
3. Physician diagnosed asthma, confirmed by patient history/report, as well as pulmonary function test (FEV1 \geq 60% of predicted or 1.5 L) and methacholine testing (Baseline methacholine PD20 < 16 mg/ml if taking ICS or < 8 mg/ml if not taking ICS at Visit 2) to confirm diagnosis.
4. Non-smoker (e.g., tobacco, e-cigarette, marijuana) for \geq 1 yr.; Nicotine patch or gum is allowed.
5. \leq 10 pack-year smoking history;
6. Suboptimal control of asthma as determined by a score < 19 or less on the Asthma Control Test (ACT) at Screening and Randomization Visits.
7. Ability to understand the English or Spanish language and to understand the study procedures and comply with them for the entire study period.
8. Females of childbearing potential: Pregnant or lactating; participants of appropriate age will be screened with urine pregnancy tests at each visit and cannot participate if pregnant. Participants must agree to use effective contraception during the trial.
- 9.

Prior Medical Therapy

Washouts:

The chart below lists medications/substances that decrease airway hyper-responsiveness and should not be taken prior to pulmonary function testing. Withholding times are listed next to the medication.

Medications/Substances	Withhold/Washout Times before test
Caffeine, cola drinks, and chocolate	Avoid the day of
Alcohol	4hrs
Short-acting β -agonists in conventional inhaled doses (e.g. albuterol 200 μ g)	6 hrs
Long-acting β -agonists (e.g. salmeterol)	36 hrs
Ipratropium (Atrovent 40 μ g)	12 hrs
Long-acting anti-muscarinic agents (e.g. tiotropium)	\geq 168 hrs (7days)
Ultra-long-acting β -agonists (i.e. indacaterol, vilanterol, olodaterol) Oral theophylline	24-48 hours (2 days)
Oral theophylline	12-24 Hrs

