9.6 Data Analyses

We will compare the change in log-transformed methacholine reactivity (PD₂₀) in the ginger versus the placebo group using two-sample t-test. We will compare patients' initial PD₂₀ (day 0) to their subsequent PD₂₀ at days 28, 56 using paired t-test. It is possible that the PD₂₀ measurements on days 0, 28 and 56 could be influenced by the consumption of oral ginger 1 hour prior so we will also compare the PD₂₀ at

day 0 to those at 28 and 56. An acute benefit in methacholine tolerance will be reflected in a significant improvement between PD₂₀'s at days 0, 28 and 56 while a chronic improvement will be reflected in improved PD₂₀'s at days 28 and 56 compared to day 0.

Patients with asthma have remarkably consistent fractional exhaled nitric oxide (FeNO) levels when measured over time with mild-moderate asthmatics having FeNO values of approximately 40 ± 10 ppb.²² We will consider a 25% change in FeNO as biologically significant²³ comparing each patient's initial FeNO to their subsequent FeNO at days 28, 56 using paired t-test.

Data from prior studies does not support the existence of significant differences in the intervention effect between subgroups and thus subgroup analysis will not be performed.

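### The FeNO sample size of 16 per arm matches neither FeNO success rule in Section 1.1, and it rests on a FeNO level that conflicts with Section 9.6

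*Combined protocol and SAP*

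**What the plan says.** Section 1.1 gives FeNO, one of two primary endpoints, two success rules that depend on baseline: a 20% decrease above 50 ppb, and "a decrease of 10 ppb for subjects starting at a baseline of <50 ppb". The Section 3 table repeats both in one row ("20% decr for >50 ppb or decr of 10ppb for <50ppb"). It sets beside them literature values of 74 ± 37 and 37 ± 34 ppb and a size of 16 per group.

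Section 9.2 names only the upper rule: "For exhaled nitric oxide with baselines starting at >50ppb, a 20% decrease is considered clinically significant". It continues "We expect a S.D. of ~ 37", says the investigators "aim to achieve 80% power at the 0.05 level", and concludes that they "will thus require 16 subjects for each of two arms". With 10% attrition this becomes 36 participants. Methacholine alone would have needed 32.

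Section 9.6 describes mild-moderate asthmatics as having "FeNO values of approximately 40 ± 10 ppb". It introduces a third threshold, a 25% change, and for FeNO names only within-patient paired t-tests.

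Neither Section 4.1 nor Section 4.2 has a FeNO criterion. FeNO is first measured at Visit 3, where the procedure list in Section 6.2.4 puts randomization before it. Under Section 9.3, all randomized participants enter the primary analysis.

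**The concern.** FeNO drives the total sample size, so the reader should be able to tell what effect the trial can detect in the patients it admits. Three features prevent that.

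- The effect named in Section 9.2 (a 20% decrease) is not the effect that yields 16.
- The rule for baselines below 50 ppb has no sizing.
- The baseline level behind the sizing (74 ± 37) and the level in Section 9.6 (about 40 ± 10) imply very different splits of participants between the two rules.

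At stake is the reading of a null FeNO result. A plan that claims 80% power invites the conclusion that a clinically significant effect was ruled out, and that conclusion would be unsafe if the real power for either rule is far lower.

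**Working it through.** **Inputs.** Alpha 0.05, power 80%, SD about 37 and 16 per arm (Section 9.2); means 74 and 37 ppb with SDs 37 and 34 (Section 3 table); rules of 20% and 10 ppb (Section 1.1); 40 ± 10 ppb (Section 9.6). Sidedness is not stated; two-sided is assumed.

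**1. Reproduce the plan's figure.** Normal approximation: n per arm = 2 × (1.96 + 0.8416)² × (SD/difference)².
- Difference 74 − 37 = 37, SD 37: 2 × 7.849 × 1 = 15.7, so 16 per arm. 32/0.9 = 35.6, so 36 in total. Both stated figures reproduce.
- By two-sample t-test, 16 per arm gives 78% power (16.7 per arm needed for 80%). With the pooled SD √((37² + 34²)/2) = 35.5, power is 81%.
- The difference sized is 37/74 = 50% of baseline.

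**2. Rule above 50 ppb.** 20% of 74 = 14.8 ppb. At SD 37, n = 15.7 × (37/14.8)² = 98.1, so 99 per arm (about 100 by t-test). Power with 16 per arm is about 19%.

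**3. Rule below 50 ppb.** Difference 10 ppb, two-sample t-test, 16 per arm. SDs of 15 and 20 are illustrative; the documents do not give them.

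| SD of change (ppb) | Power for 10 ppb | Detectable difference at 80% power (ppb) |
|---|---|---|
| 10 | 78% | 10.2 |
| 15 | 45% | 15.4 |
| 20 | 28% | 20.5 |
| 34 | 13% | 34.8 |
| 37 | 11% | 37.9 |

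The SD 10 row matches step 1 because 10/10 and 37/37 are both a standardized difference of 1.

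**4. Dependence on correlation.** The plan does not say whether its SDs describe levels or changes. If they describe levels, SD of change = SD × √(2(1 − r)), with r the baseline/follow-up correlation, which the documents do not give.

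| r | From SD 10: SD of change; power for 10 ppb | From SD 37: SD of change; power for 14.8 ppb; power for 10 ppb |
|---|---|---|
| 0.3 | 11.8; 64% | 43.8; 15%; 10% |
| 0.5 | 10.0; 78% | 37.0; 19%; 11% |
| 0.7 | 7.7; 94% | 28.7; 29%; 16% |

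**5. Participants below 50 ppb, of 36.** Normal model, with ± read as an SD:
- 74 ± 37: Φ((50 − 74)/37) = 0.258, so 9.3 (lognormal 9.9).
- 40 ± 10: Φ((50 − 40)/10) = 0.841, so 30.3 (lognormal 30.5).

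**6. Size of the lower branch.** If 30 of 36 fall below 50 ppb, that is 15 per arm randomized, or 15 × 0.9 = 13.5 after attrition. At SD of change 10, power for 10 ppb is then 75% or 70%, rather than the 78% that needs all 16.

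**The case against.** Four arguments favour the plan, and each stands in part.

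- **The arithmetic is sound.** 16 and 36 both follow from the table means. The fault is that those inputs do not correspond to the stated success rules.
- **Section 9.6 does not forecast this trial's baseline.** Its 40 ± 10 is a literature value for mild-moderate asthma, given in a sentence about consistency over time, and ± is not defined as an SD. The trial admits mild to severe, poorly controlled asthma. A reader might infer that about 30 of 36 participants will fall below 50 ppb. The documents support that only as one end of a range whose other end is about 9.
- **An uncalculated rule need not be underpowered.** With an SD of change of 10, 16 per arm comes close to 80% for 10 ppb. What the documents lack is any basis for choosing between that SD and 37.
- **The trial is a pilot.** That would excuse low power openly stated. It does not excuse a claim of 80% power that does not apply to the endpoint as defined.

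Two further readings go too far. One is that the group above 50 ppb was properly sized and only the lower group neglected. Step 2 shows that the upper rule was not sized either, and 74 ± 37 itself places about a quarter of patients below 50 ppb. The other is that the 74 ppb figure comes from steroid-free patients and so cannot apply here. Section 4.1 does list "Treatment with inhaled corticosteroids (ICS") as a criterion, but the source patients' treatment at baseline cannot be established from a reference title. Section 4.1 also sets a methacholine limit for people not taking inhaled steroid.

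**Conclusion.** The point holds: the stated FeNO sample size supports neither success rule on the plan's own SD of about 37. Power with 16 per arm is about 78% for the 37 ppb difference actually used, about 19% for a 20% decrease from 74 ppb, and about 11% for a 10 ppb decrease. The last figure rises to about 78% only if the SD of change is 10 and all 16 per arm contribute. The plan's two FeNO levels conflict, and nothing at entry determines which rule most participants will fall under.

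These figures assume a two-sided two-sample comparison, which Section 9.6 does not name for FeNO, and SDs that apply to change. The unknown SD of change has the largest influence on the result. The documents do not establish that the trial is underpowered for the lower rule, or that most participants will fall under it.

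**What to change.** 1. Reconcile the Section 3 table, Section 9.2 and Section 9.6 to one FeNO baseline and one SD of change, justified for the patients Section 4.1 admits. Reconcile the 25% threshold in Section 9.6 with Section 1.1, and assign a baseline of exactly 50 ppb, which neither rule covers.
2. Replace the 80% power statement for FeNO with what 16 per arm can detect, as a range over the SD assumptions (in ppb, from 10.2 at SD 10 to 37.9 at SD 37).
3. Make the primary FeNO analysis a between-arm comparison of change in log FeNO, with log baseline FeNO as covariate, in all randomized participants. One analysis then covers every baseline. Report results by the 50 ppb cut as descriptive.
4. State the detectable effect on that same log scale: about 1.02 times the baseline-adjusted SD of log change with 16 per arm at 80% power. The ppb power figures do not carry over to a log analysis.

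The cost is a less favourable stated power and a small change to the analysis text. Baseline FeNO is already collected at Visit 3, so no patients or measurements are added.

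### Section 9.2's 16 per arm gives about 20% power, not 80%, for a 20% FeNO decrease with SD about 37 ppb; 16 per arm fits a difference of about 37 to 38 ppb

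*Combined protocol and SAP*

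**What the plan says.** Section 9.2 gives the effect of interest first: "For exhaled nitric oxide with baselines starting at >50ppb, a 20% decrease is considered clinically significant". The next sentence sets the SD, power and sample size: "We expect a S.D. of ~ 37 and aim to achieve 80% power at the 0.05 level and will thus require 16 subjects" for each of the two arms. No other FeNO effect appears in that section. It refers to the table in Section 3, where the FeNO row holds the 20% (above 50 ppb) or 10 ppb (below 50 ppb) threshold, literature values of 74 ± 37 and 37 ± 34 ppb, and 16 per group.

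Section 1.1 uses the same two-part criterion. For lower baselines it is "a decrease of 10 ppb for subjects starting at a baseline of <50 ppb".

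Section 9.6 differs on three counts:

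- It describes FeNO as stable over time, "with mild-moderate asthmatics having FeNO values of approximately 40 ± 10 ppb".
- It sets another threshold: "We will consider a 25% change in FeNO as biologically significant".
- The only FeNO test it lists is within patient, comparing each patient's "initial FeNO to their subsequent FeNO at days 28, 56 using paired t-test". A two-sample test between arms is specified for the change in log PD20 but not for FeNO.

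**The concern.** A reader of Section 9.2 will take the 80% power as applying to a 20% fall in FeNO, because that is the only effect named and the sample size is presented as following from it. A 20% fall from a baseline in the range the section describes is small beside an SD of 37 ppb, and 16 per arm is far too few to detect it with that power.

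FeNO is one of two primary outcomes, and it moves the requirement from 14 to 16 per arm. If the power is overstated, a non-significant FeNO result could be read as evidence that ginger has no worthwhile effect, when the trial had little chance of showing one. Section 9.6 adds to the difficulty: neither its test nor its threshold is the one on which the two-arm calculation rests.

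**Working it through.** **Inputs.** SD 37 ppb, 80% power, alpha 0.05 and 16 per arm (Section 9.2); means 74 and 37 ppb with SDs 37 and 34 (Section 3 table); 1:1 allocation; 18 per arm after 10% attrition. Sidedness is not stated, so I take it as two-sided.

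**Step 1: reproduce the 16.** The normal formula is n per arm = 2(1.960 + 0.842)² × (SD/Δ)² = 15.70 × (SD/Δ)².

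- Δ = 74 − 37 = 37 and SD 37: 15.70 × 1 = 15.7, so 16.
- Same Δ with pooled SD √((37² + 34²)/2) = 35.5: the t-test needs 16 and has 81.3% power.
- Same Δ with SD 37 under the t-test: 17 needed; 16 gives 78.1%.

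So 16 follows from the table's 37 ppb contrast, a 50% fall. The methacholine row behaves the same way: 1.73 − 1.07 = 0.66 with SD 0.6 gives 80.0% power at the stated 14 per arm, whereas the 0.7 criterion would need only 13. That both rows were sized on the literature contrast is an inference; no section says so.

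**Step 2: the effect named in Section 9.2.** Δ = 0.20 × 74 = 14.8 ppb, so SD/Δ = 2.5.

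- Normal formula: 15.70 × 6.25 = 98.1, so 99 per arm; t-test: 100 per arm.
- At 16 per arm the standard error is 37 × √(2/16) = 13.08 ppb, the noncentrality is 14.8/13.08 = 1.13 on 30 df, and power is 19.5%. With all 18 per arm it is 21.5%.
- A one-sided 0.05 test would give 29.5%.

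**Step 3: other effects, SD 37, 16 per arm.**

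| Effect | Δ (ppb) | Power | n per arm for 80% |
|---|---|---|---|
| 20% of 50 ppb, or the 10 ppb criterion | 10 | 11% | 216 |
| 20% of 74 ppb | 14.8 | 19% | 100 |
| 25% of 74 ppb (Section 9.6) | 18.5 | 28% | 64 |
| 20% of 100 ppb | 20 | 32% | 55 |

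The difference detectable with 80% power is 37.9 ppb with SD 37 (37.9/74 = 51% of baseline), or 36.4 ppb with the pooled SD of 35.5.

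**Step 4: change from baseline.** If the SD is 37 at both visits and the correlation is r, the SD of change is 37√(2(1 − r)). The plan gives no r, so the values below are assumptions (Δ = 14.8, 16 per arm).

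| r | SD of change (ppb) | Between-arm power, change | Paired test, one arm of 16 |
|---|---|---|---|
| 0.5 | 37.0 | 19% | 32% |
| 0.7 | 28.7 | 29% | 49% |
| 0.8 | 23.4 | 41% | 66% |
| 0.9 | 16.5 | 69% | 92% |
| 0.92 | 14.8 | 78% | 96% |
| 0.95 | 11.7 | 93% | over 99% |

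Eighty percent between arms needs an SD of change of 14.5 ppb or less (r about 0.92). Baseline-adjusted ANCOVA gives 24%, 34%, 45% and 71% at r = 0.5, 0.7, 0.8 and 0.9, and also needs about 0.92. The paired column does not compare ginger with placebo.

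**Step 5: Section 9.6's SD of 10 ppb.** Between-arm power at 16 per arm is 59% for 8 ppb (20% of 40) and 78% for 10 ppb. A 10 ppb difference with SD 10 is also one SD, and so also gives 16 by the normal formula. It does not fit Section 9.2, which specifies baselines above 50 ppb and SD about 37.

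**Step 6: precision.** The 95% CI half-width for the between-arm difference in single values is 2.042 × 13.08 = 26.7 ppb.

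**The case against.** The strongest reply is that 16 is correct for the figures in the Section 3 table, which Section 9.2 cites. The threshold for clinical significance sits in a separate column, is defined per subject in Section 1.1, and is never literally called the powered difference. This stands in part: the number was probably computed correctly from the 74 versus 37 contrast, and reading the 20% as a difference between arm means is an interpretive step. But Section 9.2 names no other FeNO effect and presents 16 as the consequence, so the text as written claims power it does not have. Even on this reply, the powered effect is 37/14.8 = 2.5 times the one called clinically significant.

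A second reply is that FeNO is stable within patients, as Section 9.6 says, so change scores would be more sensitive and 20% power is the unfavourable case. It is one scenario, and a correlation of 0.95 would give 93%. But the plan states neither a correlation nor an SD of change, 37 is the SD of single values in its table, and the paired test does not compare the arms.

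A third is that this is a pilot with a second primary outcome whose calculation is unaffected. That is a reason not to enlarge the trial. It does not justify leaving a formal power claim that its own inputs contradict.

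**Conclusion.** The point holds: the power statement is wrong as written. On Section 9.2's SD and 20% effect, with the table's 74 ppb baseline, 16 per arm gives about 20% power (11% to 32% for baselines of 50 to 100 ppb), and 80% would need about 100 per arm. Sixteen per arm suits a between-arm difference of about 37 to 38 ppb. With a CI half-width near 27 ppb, a non-significant result could be compatible with both no effect and a 20% decrease.

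These figures assume a two-sided 0.05 two-sample t-test on single values with SD 37. The conclusion survives a one-sided test, SDs of 34 to 37 and 18 per arm. It would change only if the sponsor can support an SD of change of about 14.5 ppb or less. The correction is essential because FeNO is a primary outcome and determines the sample size.

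**What to change.** Keep 36 patients and make these changes:

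1. **Sections 3 and 9.2.** State that 16 per arm gives about 80% power for a between-arm FeNO difference of about 38 ppb with SD 37 (about 36 ppb with the table's pooled SD). State that power for a 20% decrease from 74 ppb (14.8 ppb) is about 20%, so a non-significant FeNO result is not evidence against a clinically significant effect. If change from baseline was intended, give the SD of change and its source instead; 80% power for 14.8 ppb at 16 per arm requires 14.5 ppb or less.
2. **Section 9.6.** Name the between-arm FeNO test to which the power refers, for example the two-sample t-test on change already planned for PD20, and report the between-arm difference with a 95% CI.
3. **Consistency.** Reconcile 74 ± 37 with 40 ± 10 ppb, and the 20% or 10 ppb criterion with the 25% in Section 9.6.

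The cost is wording in three sections, a commitment to one FeNO test before unblinding, and a less favourable stated power. No patients, visits or measurements are added.
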